Inclusion criteria: (a) 75 outpatient men and women between the ages of 40 and 75; (b) English speaking; (c) live independently within a 60 mile radius of Atlanta; (d) meet education corrected cut-offs on the MMSE indicating cognitive impairment (score of 20 for 8-9 yrs of schooling; 22 for 10-12 yrs of schooling; 23 for >12 yrs)¹⁰²; (e) have a computer with internet connection; (f) documented medical diagnosis of NYHA class II or III systolic. (g) Left ventricular ejection fraction (LVEF) $\geq 10\%$ that is documented within the last year by echocardiogram, cardiac catheterization ventriculography or radionuclide ventriculography; (h) Receiving medication therapy for HF according to American College of Cardiology (ACC) American Heart recommendation guidelines¹⁰³ for at least 8 weeks prior to study enrollment. Exclusion criteria: a) NYHA class I or IV; (b) change in HF therapy within 8 weeks; (c) worsening HF symptoms within last 5 days; (d) unstable angina; (e) renal insufficiency (serum creatinine > 3.0 mg/dL); (f) fixed rate pacemaker; (g) uncontrolled hypertension; (h) not involved in any structured exercise program or exercising 3 or more times per week for a minimum of 30 minutes and; (i) not hospitalized within the last 30-days; (j) not diagnosed with any neurological disorder that may interfere with cognitive function; (k) Beck Depression Inventory II (BDI-II) score greater than 25; and (l) any disorder interfering with exercise participation.

It is anticipated that approximately 50% of patients approached regarding the study will be eligible and will agree to participate. Based on the PI's earlier studies, a retention rate of 85% is expected. The actual acceptance and retention rates will be included as part of the information gleaned from this feasibility study to inform the design and methods for a subsequent, large scale efficacy trial.

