Rationale for sample characteristics. The age range was selected to avoid confounding effects of age and sarcopenia with outcomes such as aerobic capacity, BDNF and HRQOL; participants below the age of 40 years are likely to have HF for other reasons than the majority of the general HF population. Older age (>75) is associated with reduced exercise capacity and age related cognitive decline which may confound physical function cognitive outcome measurement. In addition, persons over the age of 75 are at higher risk for adverse events during exercise testing and with aerobic exercise. Although we anticipate most participants to be receiving optimal medication therapy, treatment decisions regarding individual care will be based on patient's clinician; evidence-based care will be encouraged. If any participants are not being treated with what is considered optimal medication therapy according to ACC guidelines, the reason (eg, intolerance) will be recorded and tracked by group and statistically controlled as a covariate. We recognize that both resting and exercise heart rates are influenced by beta-blockers, which is considered optimal therapy for HF patients. For both exercise testing and training we will use the heart rate reserve method which takes into account the patient's resting heart rate, thereby reducing the effect of beta-blockade. We will attempt to schedule patients for their exercise testing and training a minimum of 3 hours after taking beta blockers.²⁸⁻²⁹ For patients who are unable to schedule exercise during this time frame or exercise up to the prescribed heart rate, Borg's 6-20 rate of perceived exertion scale (RPE) between 12-15, will be used to guide exercise intensity, consistent with a moderate intensity level exercise. Patients with an ICD may be enrolled if their heart rate limits are set to be higher than the target heart rate for the exercise regimen. In our last preliminary study, approximately 90% had an ICD; there were no firings during exercise or any increase in adverse events. Although unlikely to occur, participants with a fixed rate pacemaker would not be able to participate because heart rate may be set at a lower rate than required to achieve prescribed target heart rate. Participants who have recurrent angina, more severe symptoms have uncontrolled hypertension will be excluded due to the higher risk for adverse cardiovascular events during exercise testing and the walking intervention. Because moderate to severe depressive symptoms are a major predictor of exercise attrition and more severe CI, participants will be excluded who have a BDI-II score of 25 or higher. These severely depressed subjects will be evaluated for suicidal risk, and referred to psychiatric care. Because the benefit of exercise is being evaluated, participants who are currently enrolled, or were recently enrolled in an exercise program for the past 8 weeks, currently exercising at regular intervals (more than twice per week for 30 minutes) will not be eligible for the study.

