The study was designed to minimize and protect against potential risks by careful training of staff, emphasis on confidentiality, and efforts to increase convenience to the subject for each study activity. To reduce anxiety and emotional responses to the intervention, we will address these concerns as part of the sessions. In the rare event that subjects experience emotional distress, they will be referred to their provider, a clinical psychologist or clinical nurse specialist available to HF patients. The total BDI-II will be reviewed as part of screening and those with moderate to severe depressive symptoms will be excluded. If BDI-II scores reveal that moderate depression (BDI-II>25) is present, the participant will be informed and asked for permission to share this information with their primary physician because of the established increased CV risk as a consequence of depression in this patient population. This will be a part of the study explanation prior to informed consent. It is important to note that the BDI-II does not confer a diagnosis of clinical depression but is a useful screening tool for those needing further assessment by a clinical psychologist or psychiatrist.

All patient records will be kept in a locked file cabinet in the research office and will be accessible only to the PI and the research team. All data will be coded by subject identification number, and no identifying information will be recorded on the data collection forms. The master list that will connect the codes to identifying information will be secured in the research project office. All data maintained in the computerized database will be accessible only with a login and protected, encrypted password. After the study is completed, all data will be kept according to regulations in a locked file.

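### Exclusion items (h) to (j) are worded as conditions for entry, and the protocol is inconsistent on a BDI-II score of exactly 25 and on an 8-week exercise look-back

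*Combined protocol and SAP*

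**What the plan says.** Section E (Human Subjects Research) lists twelve exclusion criteria, (a) to (l). Nine of them, (a) to (g), (k) and (l), name a condition that keeps a patient out. The other three are worded the other way round. The exercise item reads "h) not involved in any structured exercise program or exercising 3 or more times per week for a minimum of 30 minutes". The two items that come next in the list follow the same pattern: "i) not hospitalized within the last 30-days; (j) not diagnosed with any neurological disorder that may interfere with cognitive function".

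The Rationale for sample characteristics, in the same section, returns to exercise. It bars "participants who are currently enrolled, or were recently enrolled in an exercise program for the past 8 weeks" and adds that those "currently exercising at regular intervals (more than twice per week for 30 minutes) will not be eligible for the study".

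The BDI-II cut-off appears in three places:

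- Exclusion item (k): "Beck Depression Inventory II (BDI-II) score greater than 25".
- Rationale for sample characteristics: "participants will be excluded who have a BDI-II score of 25 or higher".
- The Section E text on minimizing and protecting against risks: it first says, without a number, that moderate to severe depressive symptoms lead to exclusion, and then continues "If BDI-II scores reveal that moderate depression (BDI-II>25) is present", which triggers telling the participant and asking permission to tell the primary physician.

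After the criteria, the protocol anticipates that "approximately 50% of patients approached regarding the study will be eligible and will agree to participate" and says the actual acceptance rate will inform the later efficacy trial.

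**The concern.** These are operative entry rules, and as written they are wrong or inconsistent in three ways.

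1. Under an exclusion heading, a *not* reverses the item. Taken literally, (h) to (j) remove the patients the trial evidently wants and do not remove those it wants to keep out. Item (j) bears directly on Aim 2, where the outcome is cognitive ability.
2. One BDI-II score is eligible under one statement and ineligible under another. It also falls under different follow-up steps: the Rationale attaches a suicide-risk evaluation and psychiatric referral to its excluded group, and the risk-protection text attaches notification to its own threshold.
3. A rule on recent exercise-programme enrolment appears only in the Rationale, although it protects the comparison of the exercise arms with attention control.

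No order of precedence is stated. Clinicians at the enrolling clinics identify candidates and databases are searched as well, so the criteria are applied by more people than the core team. The acceptance rate that the study will report depends on which version they used.

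**Working it through.** The protocol gives no figure to reproduce here. The check compares the statements as logical rules.

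**Direction of (h) to (j).** There are 12 exclusion items, and 3 of them carry the misplaced *not*. An inactive patient outside any programme, with no hospital stay in the last 30 days and no neurological disorder, meets (h), (i) and (j): 3 of 12.

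**Item (h) against the Rationale.** Let P = in a structured exercise programme and F = exercising at least 3 times a week. The look-back is left aside, and the two sections' terms for a programme are treated as the same.

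- Rationale, items read as alternatives: exclude if P or F.
- (h), *not* covering both limbs: exclude if not (P or F).
- (h), *not* covering only the first limb: exclude if (not P) or F.

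| P | F | Rationale excludes | (h), both limbs | (h), first limb only |
|---|---|---|---|---|
| no | no | no | yes | yes |
| no | yes | yes | no | yes |
| yes | no | yes | no | no |
| yes | yes | yes | no | yes |

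Item (h) gives the opposite answer in 4 of 4 rows on the first reading and 2 of 4 on the second. Two rows fail on both: the inactive non-member is excluded, and the programme member exercising fewer than 3 times a week is not.

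The Rationale sentence has no connecting word before its last clause. If it is read instead as requiring both conditions (exclude if P and F), its column becomes no, no, no, yes. Then (h) disagrees in 2 of 4 rows on either reading (rows 1 and 4 for both limbs; rows 1 and 2 for the first limb only). The inactive non-member is wrongly excluded in every case.

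**Exercise frequency.** For whole sessions per week, at least 3 and more than 2 are the same rule, so there is no conflict here.

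**BDI-II, integer scores.**

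| Score | Item (k): > 25 | Rationale: >= 25 | Risk protection: > 25 |
|---|---|---|---|
| 24 or less | not met | not met | not met |
| 25 | not met | met | not met |
| 26 or more | met | met | met |

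The statements differ at exactly one score, 25. The documents give no frequency for it.

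**Look-back.** Take a patient who left a programme four weeks ago and is now inactive. If the Rationale means any enrolment within the past 8 weeks, this patient is barred. If it means enrolment throughout those weeks, the patient is not. Item (h), with its direction corrected, has no window and does not bar the patient. The only 8-week windows in the criteria lists concern heart-failure medication or a change in therapy. The number of patients affected cannot be derived from the documents.

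**The case against.** The best case against is that nobody would screen by the literal text. The target population is stable class II and III heart failure, and item (c) removes recent worsening, so requiring a recent hospital stay would be incoherent. The qualifier in (j) about interference with cognition makes sense only as a reason to keep patients out. A criterion stated once is normal. On this view the stray *not* is a copy-edit, the row counts for (h) describe readings that no one would apply, and what remains is one integer score and an omitted look-back. The > 25 in the risk-protection text is also attached to notification, not directly to exclusion.

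Much of this stands. Reversal at screening is unlikely. The row counts are logical cases, not patients, and the 4 of 4 figure depends on reading the Rationale's items as alternatives. The look-back is an omission in the list, not a clash between two windows. The sharpest eligibility conflict on the BDI-II is between item (k) and the Rationale.

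It does not clear the text. The intent of (i) and (j) has to be inferred, because nothing else states it. The risk-protection text labels scores above 25 as moderate depression directly after saying that moderate to severe symptoms are excluded, so it bears on the exclusion boundary as well as on notification. Common sense cannot settle the boundary or the look-back, because both versions are plausible.

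**Conclusion.** The concern holds. Three of the twelve exclusion items are worded in the wrong direction. One of them, (h), is contradicted by the Rationale; the other two rest on inferred intent. The BDI-II statements disagree at a score of 25 only. The 8-week look-back appears in one place and is ambiguous there.

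The practical effect on enrolment and on the acceptance rate is probably small, but it cannot be quantified from the documents, and no power or sample-size figure changes. The correction should be made because these are operative entry rules and because the acceptance rate is a feasibility result that needs a single definition. The conclusion rests on the text alone. Only the row counts for (h) need the further assumptions stated with them.

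**What to change.** - Reword (h), (i) and (j) as positive exclusions, or move them to the inclusion list with the *not* kept. For (h), take the direction from the Rationale; the frequency thresholds already agree. Have the investigators confirm (i) and (j).
- Reconcile the BDI-II boundary across item (k), the Rationale and the risk-protection text to one operator and value chosen by the investigators, and check that the follow-up steps attached to it still line up.
- Decide whether the 8-week look-back applies. If it does, state it in (h) so that it is clear whether any enrolment in the window or enrolment throughout it counts, and match the Rationale. If it does not, remove it from the Rationale.
- If screening has begun, record which version was applied, so that the reported acceptance rate has a defined basis.

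The cost is a wording amendment and a screening-form edit. The boundary and look-back decisions may change eligibility for a few patients.

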confounding variable of receiving attention from a healthcare professional. Instruction on stretching and flexibility movements is also expected to reduce attrition and patient dissatisfaction and to better ensure concealment of group allocation. These time-equivalent, flexibility/stretching movements have been previously piloted and will serve as the “placebo exercise condition.” In pilot evaluations they were well received, but were not strong enough to influence outcomes. The AC education placebo component will be delivered as soon as feasible after baseline (T1). The first 2 weeks of the intervention phase will include 2 home visits to demonstrate stretching and flexibility movements and to discuss educational materials. Weekly telephone calls will then be made for the next 10 weeks to discuss educational materials and to answer questions about stretching movements. An appointment will be made for participants to come to the ACTSI to collect T2 measures; this will occur at weeks 13 and 14. From weeks 15-24 bi-monthly telephone contact will be used to encourage continued adherence to the AC intervention. At the end of 24 weeks, a final visit to the ACTSI will be arranged and T3 measures will be taken. For ethical and cardiovascular health reasons, the AC group will be advised to exercise, but will not be provided with an exercise prescription or self-monitoring equipment since these have been shown to influence exercise adherence and exercise self-efficacy and may confound study outcomes.¹⁰⁴⁻¹⁰⁵

Groups 2 and 3 Exercise Prescription. Groups 2 & 3 will receive the same exercise prescription using a progressive moderate intensity aerobic protocol. To ensure that participants achieve adequate training stimulus, dose-specific exercise will be based on maximum heart rate (HR) obtained during symptom limited, modified Balke treadmill tests¹⁰⁶⁻¹⁰⁷ conducted by an exercise physiologist and supervising cardiologist in the

	Wk 1-2	Wk 3-4	Wk 5-7	Wk 8-9	Wk 10-12
Intensity	60%	60%	70%	70%	70%
Duration	30 mins	45 mins	45 mins	45 mins	45 mins
Frequency	3 x/wk	3 x/wk	3 x/wk	3 x/wk	3 x/wk

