CIN. Target heart rate (THR) using the 60% to 70% of maximum HR achieved on the cardiopulmonary exercise test (CPET) will be used to monitor the intensity and training response for aerobic exercise. Each participant will be provided with an individualized THR zone based on CPET results.¹⁰⁷ Under the supervision of a research nurse, participants will begin the walking sessions at 60% of THR and increase to 70% by week 5 as shown in Table 2. In our pilot with HF patients, a progressive moderate intensity level exercise program yielded positive outcomes with no adverse events, was appealing to participants and adherence rates were 80% or higher.

Group 2: EX/CT (UC + aerobic exercise + cognitive training) The first 2 weeks of the study will consist of 2 consecutive weekly home visits by the research nurse to demonstrate use of the HR monitor, pedometer and the CT program, Brain Fitness (Posit, San Francisco, CA detailed below). The research nurse will supervise one walking session during the first 2 weeks to ensure the safety of the participant and that he/she understands how to use the Polar HR monitor and pedometer and how to complete the walking logs. During the first 2 weeks, the research nurse will also provide training and demonstrate how to use the Brain Fitness computerized cognitive training program designed to be completed in 40 sessions over 12 weeks. We expect that participants will require additional time (at least 30 minutes each time) in the first 2 weeks to learn how to use and access the Brain Fitness program. The weekly schedules are provided in table 1.

The weekly schedules are provided in table 1.

Brain Fitness Computer Training: is based on the principles of positive brain plasticity and designed for use by adults. The training program (“Brain Fitness”) is focused on speech reception to strengthen an individual’s memory for speech. It has 6 modules names Hi-Lo, Tell Us Apart, Match It, Listen and Do, Sound Replay and Story Teller. Research to date has found: 1) participants with limited or no computer experience were capable of learning to perform the training exercises, 2) the training was safe and well tolerated by participants, and 3) healthy participants who trained on Brain Fitness showed on average a 1/3 standard deviation of improvement in memory, concentration and cognition, and 4) it has been tolerated well in patients in HF in a prior study.¹⁶

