Exercise Adherence	Polar HR (intensity, duration and frequency), walk calendars, pedometer, nurse telephonic log	10 minutes	3 and 6 months
CT adherence	Brain Fitness program, nurse telephonic log	NA	

Physical Function will be assessed using the **modified Balke maximal treadmill test** ¹⁰⁶⁻¹⁰⁷ to determine peak oxygen consumption (peak VO_2), maximum HR for exercise prescription and to screen for cardiac contraindications to exercise according to the (AHA/ACC) guidelines. ¹⁰² **Physiological status.** The serum biomarker **BDNF** will be collected in the CIN by a research nurse or phlebotomist, the assays will be stored at -80 degrees until processed by the ACTSI biocore lab using the manufacturer's ELISA guidelines.

QOL. The **Kansas City Cardiomyopathy Questionnaire (KCCQ)** ¹¹⁰ is a reliable and well validated 23-item, disease specific questionnaire that quantifies physical function, symptoms, social function, and HRQOL in HF. ¹¹¹⁻¹¹²

Adherence. Step counts will be indirectly assessed using the Omron HJ-7201ITC pedometer to count daily steps. ¹¹³⁻¹¹⁷ The 15 point (6-20) **Borg Rate of Perceived Exertion (RPE) Scale** ¹¹⁸ will be used to measure participants' subjective perception of effort. **Target heart range (THR)** ¹⁰⁷ using the HR reserve method will be used to monitor the intensity and training response to walking. Polar Beat ® Watch (FT4) ¹¹⁹ will be used to monitor intensity and duration of walking. ¹²⁰⁻¹²¹ Actual adherence to intervention protocols and study attrition rates will be included in an intent-to-treat analysis (CT & Ex).

Acceptability. During post-baseline visits and phone contacts, participant's opinions about the intervention, e.g. perceived usefulness, ease of use, barriers to adherence, perceived improvements in health, cognition, mood, quality of life will be collected. The PI will use content analytic techniques to assess acceptability and to identify themes suggesting possible revisions or alterations in the interventions that might improve acceptability.

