Procedures Recruitment, Screening and Enrollment of participants will occur through physician and other health care provider referrals and patient self-referral. These methods have proved successful in our prior work. The recruitment nurse will arrange a time for laboratory, and treadmill tests at the CIN. Baseline (T1) measures will be taken in the CIN by a trained data collector blinded to group assignment. All participants will be given the same measures, in the same sequence at each time point. Questionnaire completion should take 30 minutes or less, the neuropsychological testing is anticipated to take 75 minutes. Laboratory samples will be taken prior to the treadmill test. The BDNF samples will be stored at -80 in the CIN until processed. After the laboratory work is completed, the modified Balke treadmill test will be conducted by an exercise physiologist; emergency equipment, doctors and nurses are available. After BL, participants will be randomized to study groups by computerized sheet prepared by the study statistician. At 3 and 6 months we will follow the same procedures used at Evaluation 1. After Evaluation 3, participants will be discharged from the study, and all participants provided with study results. A \$50 honorarium will be provided at each measurement time point, to total \$150/patient for completing the study. Intervention process measures (evaluation, attendance) will be tracked and evaluated to maintain internal validity. Protocol adherence will be calculated for both groups.

Data Management and Analysis. The Biobehavioral and Methods Core (BMC) will coordinate the collection, integration, and analysis of biological and psychosocial data for this study. Data will be analyzed using both descriptive and inferential test statistics. We will build multivariable statistical models to examine the relationship between an Ex/CT intervention to exercise alone and attention control (AC) on cognitive functioning (P-30 Neuropsychological Battery), cerebral oxygenation (NIRS, 3 months only), physiological status (BDNF), physical function (peak VO_2) and QOL (KCCQ) in HF at BL, 3 and 6 months controlling for but not limited to age, gender, SES, depression, social support, NYHA class, medications and comorbidities.

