The potential risks associated with the walking intervention are anticipated to be minimal. Any potential cardiovascular (CV) events that poses risk to the participant is anticipated to be detected during the modified Balke maximal treadmill test. In addition, the duration of walking will be limited to 30 minutes during the first 2 weeks and at an intensity level (60%) that is not likely to result in any adverse CV events; if necessary participants can rest as needed until the 30 minute duration of walking is completed. Participants will wear a Polar HR monitor so that HR and intensity level can be closely monitored. Participants will undergo 2 supervised walking sessions prior to walking at home unsupervised; the risk associated with the unsupervised session therefore, is anticipated to be minimal. Participants in the study will be provided with detailed instructions on self-monitoring HR, BP and symptoms associated before, during and after walking. Each participant will be provided with a target heart rate range to stay within during the study period. Participants will be instructed to wear the Polar HR monitor during each exercise session. The participants will take their HR, and BP (if machine available) and weight prior to and after each walking session and record it in their walking calendar. Participants will be instructed to call the research nurse if their BP or HR is outside their normal range. If participants are symptomatic, experience increased shortness of breath or have a greater than 2 pound weight gain over the previous 24 hours, they will be instructed not to exercise. The participants will be instructed to take their medications as usual prior to exercise and instructed on proper attire for exercising. Demonstrations and return demonstrations of the Polar HR monitor will ensure they know how to wear the monitor around the chest as well as trouble shoot when the monitor does not display a HR. They will be instructed that if their HR approaches within 5-10 beats of the target HR range to slow the walking pace down. They will also be instructed if they have an ICD, to keep their HR 15 beats below the firing range at all times (usually set at higher than 170 beats per minute, so it is unlikely to interfere with training stimulus). In addition, they will be instructed to monitor their RPE using the Borg 6 to 20 scale, and to keep their RPE at 12-13 during the initial weeks and to gradually progress with instructions to 15 as stipulated in the protocol. Participants in the intervention groups will be advised to carry a cell phone when they walk at home in the event of an emergency or sudden event. Specifically, participants will be instructed to slow their pace if their HR increases to near THR as previously noted or if they become short of breath. Participants who have ischemic heart disease and prescribed nitroglycerin (NTG) will be instructed to carry their NTG with them during each walking sessions. If chest pain occurs during exercise, the participants will be told to stop exercising and to take a NTG as directed by their cardiologist. The participant will also be instructed if the chest pain continues to sit down and to call a relative or friend and to take another NTG if the chest pain does not subside. If the chest pain continues and is not relieved by NTG within 10 minutes they will be instructed to call 911. If the participant becomes moderately to severely dyspneic where they cannot talk while walking they will be instructed to stop walking until the dyspnea subsides. If the dyspnea continues once they have stopped walking for several minutes they will be instructed to call a relative or friend; if not dissipated they will be

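### The ICD entry rule has no beat margin, unlike the plan's own 15-beat walking rule, and compares the device limit with the training target although the treadmill test, which has no written device-based stop, goes above it

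*Combined protocol and SAP*

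**What the plan says.** The only ICD entry rule is in E. Human Subjects Research, under the rationale for sample characteristics: such patients "may be enrolled if their heart rate limits are set to be higher than the target heart rate for the exercise regimen". The numbered eligibility list in the same section excludes fixed-rate pacemakers and does not mention ICDs.

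The potential-risks text on the walking intervention instructs participants, "if they have an ICD, to keep their HR 15 beats below the firing range at all times", and adds that the firing range is "usually set at higher than 170 beats per minute, so it is unlikely to interfere with training stimulus". All walkers are also told "if their HR approaches within 5-10 beats of the target HR range to slow the walking pace down".

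The target comes from the baseline test. Under Groups 2 and 3 Exercise Prescription, dose is "based on maximum heart rate (HR) obtained during symptom limited, modified Balke treadmill tests", and "Each participant will be provided with an individualized THR zone based on CPET results". The Physical Function paragraph says the test supplies "maximum HR for exercise prescription and to screen for cardiac contraindications to exercise". On order, Procedures states: "After BL, participants will be randomized to study groups by computerized sheet prepared by the study statistician".

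The potential-risks text on the treadmill test lists ICD firing among the risks. It states an immediate stop for ST elevation or multiple ventricular ectopy; other untoward vital-sign changes lead to a call to the study cardiologist. The Data and Safety Monitoring Plan adds a stop for untoward symptoms. Neither place gives a heart rate stop tied to the device.

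**The concern.** Two things do not fit together.

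- **Entry against walking.** A limit one beat above the target passes entry. That patient cannot walk at the target and also stay 15 beats below the firing range.
- **Entry against testing.** A symptom-limited test takes heart rate above a 70% training target by construction. A limit lying between target and peak passes the entry rule and is reached on the treadmill.

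At stake is an avoidable device discharge during a research test. Baseline testing comes before randomisation, so patients in all three arms are exposed. The test is repeated: Table 3 lists peak VO2 at baseline and 3 months, and the sources-of-material paragraph also implies 6 months. In the team's preliminary study about 90% of participants had an ICD. If that share holds, most participants here carry a device, though few need have one set low enough to matter.

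**Working it through.** **Inputs from the plan:** upper training intensity 70%; walking margin 15 beats; usual device setting above 170 bpm; slow-down zone 5 to 10 beats; ICD share about 90%; sample given as both 60 and 75.

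**Assumptions (not in the plan):** resting heart rate 60 to 80, peak 110 to 150.

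The plan describes the target both as a percentage of maximum (exercise prescription) and by heart rate reserve (adherence paragraph and sample rationale). Both are shown. There is no planned figure to reproduce.

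**1. How far the test goes above the target**
- Heart rate reserve: target = rest + 0.70 × (peak − rest), so peak − target = 0.30 × (peak − rest). Lowest: 0.30 × (110 − 80) = 9. Highest: 0.30 × (150 − 60) = 27.
- Percent of maximum: peak − target = 0.30 × peak, from 0.30 × 110 = 33 to 0.30 × 150 = 45.

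These are also the widths, in beats, of the band of device limits that pass entry yet are reached on the test.

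**2. Worked case: rest 70, peak 130**
- Heart rate reserve target: 70 + 0.70 × 60 = 112. Limits of 113 to 130 pass entry and are reached on the test.
- Walking at 112 with a 15-beat margin needs a limit of at least 127. If the slow-down instruction holds the walker 10 beats lower (102), the limit must be at least 117, so 113 to 116 conflict. If 5 beats lower (107), it must be at least 122, so 113 to 121 conflict.
- Percent-of-maximum target: 0.70 × 130 = 91. Limits of 92 to 130 pass entry and are reached on the test.

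**3. Where the usual setting stands**
- A limit is reached on the test only if it is at or below the patient's own peak. Over the assumed range that is 110 to 150, which is 170 − 150 = 20 to 170 − 110 = 60 beats below the usual setting.
- At a limit of 170, a test conflict needs a peak of 170 or more.
- At 170, a walking conflict needs a target above 170 − 15 = 155. By heart rate reserve that means a peak above 80 + 75/0.70 = 187 (rest 80) to 60 + 95/0.70 = 196 (rest 60); by percent of maximum, above 155/0.70 = 221.

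**4. What a test stop would do**
- At a limit of 170, a stop 15 beats below is 155, above every assumed peak, so no test is shortened. A 10-beat stop is 160.
- With 15 beats, a test is shortened only if the limit is below peak + 15, that is below 125 (peak 110) to 165 (peak 150). With 10 beats, below 120 to 160.
- Limit 120, rest 70, would-be peak 130: the 15-beat stop is 105 and the target becomes 70 + 0.70 × 35 = 94.5 instead of 112. The 10-beat stop is 110 and the target 70 + 0.70 × 40 = 98.

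**5. Records to check**
If the 90% share carries over: 0.90 × 60 = 54, or 0.90 × 75 = 67.5, about 68.

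**The case against.** The strongest reply is that the protection exists even if this rule is loose. Much of that stands.

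- **Walkers are protected.** The 15-beat instruction applies whatever the entry rule says, and the sample rationale lets perceived exertion (RPE) of 12 to 15 guide intensity when the prescribed heart rate cannot be reached. A reader might infer that the missing margin sends people to walk close to their firing range; the documents do not support that.
- **The timing is workable for training.** The target is known only after the test, but the test precedes randomisation and is itself a screening step. A reader might infer that the entry rule cannot be applied; it can, though too late to protect the patient during that first test.
- **A device check may well happen.** The cardiologist must agree to eligibility, a history and physical precede the test, the ECG is continuous, emergency staff are at hand, a supervising cardiologist is named, and conduct follows ACC/AHA guidelines. A reader might infer that patients are tested with no device check. The documents show only that none is written down, and what the guidelines require cannot be verified here.
- **The record is reassuring.** The team saw no firings during exercise, and the cited 4,411 tests produced no test-related discharge leading to hospitalisation. That lowers the expected frequency. It does not supply a check, and the second figure covers only discharges serious enough for admission.

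It can also be said that a margin written for unsupervised walking need not govern a monitored test, and that a stop costs some peak VO2 data. This is fair, and is why the size of the test margin is best left to the cardiologist. It does not explain why the entry rule uses the training target as its only yardstick.

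**Conclusion.** The point holds as an internal inconsistency and a limited gap in the safety wording. The entry rule carries no margin although the walking rule requires 15 beats, and it uses the training target where the test reaches a higher heart rate with no written device stop.

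The gap matters mainly for patients whose device limit is at or near their own peak: 110 to 150 bpm under the assumed peaks. At the usual setting above 170, neither conflict arises in that range. It would be too strong to say that only low-set devices are affected, because a participant who peaks at 170 or more could reach a device at the usual setting. The plan gives neither the distribution of device limits nor peak heart rates, so the number affected cannot be derived; it is probably small.

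Sample size is unaffected, as are analyses other than peak VO2 in the few patients whose tests the fix would shorten. Severity is minor. Confidence is moderate, because supervision and the cited guidelines may already close the gap in practice.

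**What to change.** 1. Before the baseline treadmill test, obtain the ICD detection rate from the medical record, or when the cardiologist is contacted about eligibility.
2. Have the study cardiologist set a heart rate stop below that rate for each treadmill test, for example by 10 to 15 beats, and keep the same stop at repeat tests.
3. Restate the entry rule as a device limit at least 15 beats above the training target, applied after the test and before randomisation, with RPE 12 to 15 governing below the cap. A 15-beat stop meets this automatically, since the target is below the maximum heart rate reached and that maximum is at most the limit minus 15.
4. Flag patients whose test ended at the device stop in the peak VO2 analysis.

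**Cost:** two or three sentences and one more item abstracted from records already in use, for about 54 to 68 patients if the earlier ICD share holds. The real downside falls on a few patients with low-set devices: a submaximal peak VO2, a lower prescribed target (94.5 instead of 112 in the example above), and possibly a hidden gain at repeat testing because the same stop applies. If the sponsor prefers no submaximal tests, those few would have to be screened out.
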